## **Procedures**

The study will have a total estimated duration of one year, during which each patient will participate in 12 sessions divided into 3 weekly sessions for 4 weeks (see Figure 1). Once this phase of the study has been completed, patients who had been assigned to the placebo group will be offered the possibility of receiving the equivalent

“real” treatment at the MCC free of charge. Patients who received SMT may continue at their own cost. In addition, 4 weeks after the end of the study, patients will be contacted to request that they provide data on their pain intensity and disability, as described above, as well as responses to the questionnaires proposed as follow-up. Healthy volunteers will participate in two visits, baseline and follow-up after 4 weeks.

### **Safety protocols for COVID-19**

All participants will be treated at each visit in a properly ventilated and disinfected room, including the table on which measurements will be taken and SMT will be performed. The use of the mask will be mandatory for the patients, while the investigator and his assistants will use an N95 mask at all times. Before touching the patient, the latter will be obliged to disinfect their hands with hydroalcoholic gel. At the end of the session, all surfaces and instruments will be disinfected, and the room will be completely ventilated for a minimum of 5 minutes.

Official Title:

Efficacy of Chiropractic Spinal Manipulative Therapy in Patients With
Primary Chronic Low Back Pain: a Mechanistic Randomized Controlled
Trial

NCT number: Not Available

Unique Protocol ID: SMTCLBP

Date: December 15th, 2021

Statistical analyses

The normal distribution of the data will be verified using the Kolmogorov-Smirnov test. Data deviating from normality will be transformed to obtain a normal distribution before being entered into the data analysis. The two main outcome variables (clinical pain intensity and disability related to low back pain) will be compared between groups (SMT vs. placebo) over time (baseline and session 12) using a mixed analysis of variance. Average pain intensity since the previous treatment visit and in the seven days prior to the initial visit will be the variable used for statistical analyses. With an exploratory objective, the secondary variables (PCS, CSI, BDI-II, GAD scores, PPTs, degree of pain widespreadness, urinary cytokine levels, number and severity of reported adverse effects, presence of leg pain, pain medication use) will be compared between groups (SMT vs placebo) over time (baseline and session 12) using another mixed analysis of variance. To test a priori hypotheses, significant effects will be decomposed using planned comparisons. For the rest of the effects, Tukey's HSD will be used for testing any pair-wise comparisons between group means.

Pearson's product-moment correlation analyses will be carried out to examine the association between primary variables and secondary variables that demonstrate significant effects between groups over time. Subsequently, two multiple regression models will be used to examine the predictors of improvement in clinical pain and disability over time in patients who have received SMT, using secondary variables with a significant association with the primary variables. The secondary variables used for this analysis will be: baseline PCS and CSI score, baseline PPTs in the primary pain region, baseline TNF- α levels, and baseline expectations of pain relief. In addition, in another

regression model, the changes (delta) in these variables (except expectations of pain relief, since it is only measured at baseline) throughout the 4 weeks of treatment will be used as predictor variables. This is done to identify the variables most associated with clinical evolution, in order to answer the mechanistic question.

In order to interpret the values obtained in patient groups, they will be compared with reference values obtained from the healthy controls to both CLBP groups. This will allow characterizing the patient groups to determine whether they show increased psychological symptoms, increased pain sensitivity and hyperalgesia as well as increased TNF-alpha levels compared with a reference healthy population. In order to do this, a series of mixed analyses of variance will be performed to examine differences in PPTs, urinary TNF- α levels, PCS, CSI, BDI-II and GAD scores before and after treatment between the three groups (control, SMT and placebo). To test a priori hypotheses, significant effects will be decomposed using planned comparisons. For the rest of the effects, Tukey's HSD will be used for testing any pair-wise comparisons between group means.

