### **Sample size calculation**

To determine the ideal number of participants, we have considered our first aim, which is to identify the variables linked to the CS phenotype that could help predict the response to treatment based on SMT for CLBP. In order to do this, we will perform a multiple regression analysis, using five independent variables as predictors, in particular the score on the pain catastrophizing scale (PCS) and central sensitization inventory (CSI) questionnaires (indicators of catastrophism and CS), the pressure pain thresholds (PPTs) in the primary pain area (marker of primary hyperalgesia), the urinary levels of the cytokine Tumor Necrosis Factor Alpha (TNF- $\alpha$ ; marker of inflammation) and finally the expectations of relief for each patient (indicative of potential placebo effects). The baseline values of these variables will be included in the multiple regression model. For each predictor variable, it is recommended to estimate about ten sample elements, therefore we predict that a sample size of 50 patients per group will be necessary (Ortega Calvo and Cayuela Dominguez, 2002). Taking into account two groups, one that will receive real SMT and the other placebo SMT, we will need a sample of 100 patients. An additional group of age and sex-matched healthy individuals without CLBP of the same size (50 participants) will be recruited to be used as a reference group, to determine

reference values in a healthy population for the predictor variables (questionnaires, PPTs, cytokines only)

Regarding the two main outcome variables (pain intensity and disability related to low back pain), we expect a reduction in pain and disability after one month in patients who receive 12 sessions of SMT compared to placebo. We aim to detect small to moderate effects since it is a one-month intervention in patients with chronic pain unresolved by other treatments over at least 3 months. Therefore, based on an effect size of  $f = 0.175$ , an alpha of 0.05, a power of 0.8 for 2 groups and 2 repeated measures (baseline and session 12), and a correlation between the repeated measures of 0.5, the size of the necessary sample is 34 patients per group and a total of 68 patients to detect statistically significant changes in clinical pain and disability. Therefore, our analysis based on the regression model to predict the clinical course provides us with a large enough size for both the first and second aims of this study.

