### *Clinical examination variables*

During the case history taken, data on the characteristics of the patients' CLBP will be collected. Pain intensity will be the main primary outcome. Patients will evaluate the intensity of their CLBP at the current time, as well as the mean, minimum and

maximum pain throughout the preceding seven days or since the time of the previous session, once the study is underway, according to the brief pain inventory (de Andres Ares et al., 2015; Tan et al., 2004). Pain intensity will be collected via an online questionnaire without the presence of any investigator in every visit for descriptive reasons, although only the baseline and the final values will be used for statistical analyses. The other primary outcome will be the degree of disability provoked by CLBP. Upon completing the case history, patients will fill out the Oswestry low back disability index questionnaire (Alcántara-Bumbiedro et al., 2006), which will also be completed at the end of the study.

Additionally, other pain variables will be recorded at baseline for exploratory purposes: CLBP trajectory (duration and frequency) and localization. For the later, patients will draw the area affected by their pain on a tablet, using an application (Symptom Mapper) that will allow the degree of widespreadness of their pain to be calculated (Ellingsen et al., 2021). They may also indicate any pain present of less intensity outside the low back region, as any symptom of higher intensity will necessarily exclude the patient from the study. Additionally, clinicians will determine whether the CLBP is proportionate or disproportionate to the degree or nature of the injury or pathology, with a discrete or rather diffuse distribution, according to criteria that have been defined in the literature (Nijs et al., 2015; Smart, et al., 2012). A diffuse rather than a discrete distribution has been identified as a key criterion suggesting a CS phenotype (Kosek, et al., 2021; Smart, et al., 2012).

Finally, other variables will be reported such as the intake of pain medication compatible with the selection criteria, both at baseline and at the end of treatment. Similarly, whether the patient regularly smokes will be reported at baseline, since smoking has been associated with increased serum levels of pro-inflammatory cytokines.

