#### *Adverse events reporting*

At the beginning of any of the follow-up SMT or placebo sessions, each patient will complete an online questionnaire without the presence of the investigator, answering whether they have suffered any adverse effects that they feel could be related to the treatment received. A clinical trial identified the following adverse effects as those most commonly reported after chiropractic treatment based on lumbar SMT: muscle stiffness, increased pain, radiating discomfort, and others (Walker et al., 2013). Following the example of this study, adverse effects will be classified into these categories, in addition to indicating whether they were triggered immediately, up to 24 hours, or more than 24 hours after the previous session, whether their duration was of minutes, hours (< 24 hours), between 24 and 48 hours, or longer than 48 hours (Walker, et al., 2013), and according to their intensity (very mild, mild, moderate, severe, very severe). A 3-point increase in the NRS-11 or the reporting of moderate to severe adverse events in three consecutive visits will raise the alert and the patient will be interviewed to determine whether care should be interrupted.

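### A Kolmogorov-Smirnov test on the data decides whether pain and other variables are transformed, which leaves the scale of the primary pain effect unfixed before the data are seen

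*SAP*

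**What the plan says.** The SAP's statistical analyses open with a two-step rule. First, "The normal distribution of the data will be verified using the Kolmogorov-Smirnov test". Second, "Data deviating from normality will be transformed to obtain a normal distribution before being entered into the data analysis". The next sentence names pain intensity and disability as the main outcomes, which "will be compared between groups (SMT vs. placebo) over time (baseline and session 12) using a mixed analysis of variance". Nothing exempts them from the rule.

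The SAP does not state:
- the significance level of the normality test;
- whether the critical values allow for an estimated mean and SD (Lilliefors);
- whether the test is applied per arm, per visit or to pooled data;
- which transformation is used;
- what happens if the transformation fails;
- the scale on which results are reported.

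Model residuals are not mentioned.

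The pain variable is a single average-pain rating. The protocol (Clinical examination variables) collects it "according to the brief pain inventory" and does not print the item range. The 11-point scale is named only in the adverse-event rule ("A 3-point increase in the NRS-11"). A whole-number 0-10 score is therefore an inference, though a fair one.

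**The concern.** The assumption behind a mixed ANOVA concerns the model's errors, not the raw values. A whole-number rating with 11 possible values is never exactly normal. A large enough sample will therefore fail the test because of ties, even if the underlying pain score is normal. A one-to-one transformation moves the tied values but leaves them tied, so the rule's stated aim cannot be reached for such a score.

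The scale of the primary pain analysis would then rest on a test that says little about whether the ANOVA is sound, followed by a transformation picked once the data are in hand. The group-by-time effect would no longer be in pain points. It would also not be on the scale for which the sample size was set. For TNF-alpha, a regression predictor, the same unstated choices decide whether a mildly skewed variable is transformed.

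**Working it through.** **1. The plan's own figure.** The protocol (Sample size calculation) takes f as 0.175, with 5% alpha, 80% power, two arms, two visits and "a correlation between the repeated measures of 0.5"; it arrives at 34 per group. For the within-between interaction, λ = f²·N·m/(1−ρ), with 1 and N−2 degrees of freedom.
- N = 66: λ = 0.030625 × 66 × 2 / 0.5 = 8.085, power 0.7997.
- N = 68: λ = 8.33, power 0.8116.
- N = 100: λ = 12.25, power 0.934.

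The smallest even N is 68, as stated, so the sample size is not in error. It presumes one fixed scale, because f and ρ both change under transformation.

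**2. How often the rule fires on pain.** The documents give no mean or SD for pain. Assumed: a normal underlying score with mean 5 and SD 1.5, 2 or 2.5, rounded to whole numbers and clipped to 0-10. The statistic is the largest distance between the empirical distribution and a normal with the sample mean and SD, tested at 5% (10,000 to 20,000 samples per setting; repeat runs differ by about one percentage point).

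| Flagged non-normal | SD 1.5 | SD 2 | SD 2.5 |
|---|---|---|---|
| Classical, n=50 | 21% | 5% | 1% |
| Classical, n=100 | 89% | 36% | 13% |
| Lilliefors, n=50 | 98% | 80% | 57% |
| Lilliefors, n=100 | 100% | 100% | 97% |

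The same scores left unrounded are flagged in under 0.1% (classical) or about 5% (Lilliefors). Rounding, with some clipping, drives the result. For a single assumed SD of 2, the chance of firing runs from 5% to 100% according to choices the SAP leaves open.

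**3. Stability of the verdict.** With 100 patients per visit, r = 0.5, a 1.5-point fall and classical values, baseline and session 12 get different verdicts in 19%, 47% and 29% of trials at SD 1.5, 2 and 2.5. With Lilliefors applied to each arm-by-visit cell of 50 (means 5 and 4), the four cells disagree in 7%, 59% and 85%.

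**4. Disability.** Assuming 2-point steps, mean 30 and SD 14, the test flags under 1% (classical) and 11-18% (Lilliefors) at n = 50 to 100. The problem is mainly with pain.

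**5. Is the rule needed?** On raw rounded scores (SD 2, r = 0.5), the group-by-time test has type I error 0.050 at 50 per arm and 0.053 at 34 per arm. At r = 0.5 the SD of change equals the SD of the score, so f = 0.175 is a difference in change of 0.7 SD, or 0.7 × 2 = 1.4 points. Power for that difference is 0.91 at 50 per arm and 0.77 at 34. The raw-scale analysis is sound at the planned size.

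**6. What a transformation changes.** Take SMT 6 to 3 and placebo 5 to 2.5. Raw interaction: 3 − 2.5 = 0.5 points. Log interaction: ln(6/3) − ln(5/2.5) = 0. The two scales ask different questions when baselines differ.

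**7. TNF-alpha.** The documents give no spread, so the skewness is assumed. At n = 50, lognormal data with sigma 0.5 are flagged in 11% (classical) or 70% (Lilliefors). With stronger skew even the classical test usually fires: 54% at sigma 0.8 and 80% at sigma 1.

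**The case against.** The strongest reply is that this is a wording gap with little effect on validity. Much of that stands.

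- A reader might infer that the rule inflates false positives. It does not when baselines are comparable and one transformation serves both visits: simulated type I error was 0.048 raw, 0.056 square root and 0.051 log(x+1), and a common transformation lost no power.
- The interaction example needs a 1-point baseline gap. With SD 2 and 50 per arm the standard error is 2 × √(2/50) = 0.4, so that gap is 2.5 standard errors, which is unusual after randomisation.
- A reader might infer that baseline and session 12 would be transformed differently. The SAP does not propose this. Both visits enter one ANOVA of one variable, and differing test verdicts are not differing transformations.
- A reader might infer that skewed TNF-alpha will generally slip through untransformed. That holds only for mild skew with classical critical values.
- The SAP never names a log, so the lack of a log for a pain score of 0 is not a fault in it.

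The reply leaves two things unanswered. Under either version of the test the rule often fires on pain at n = 100, and the SAP does not say what then happens to the scale of the primary result.

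**Conclusion.** The concern holds as a matter of pre-specification and interpretability, not of type I error. The rule can move the primary pain effect to an unnamed scale chosen after the data are seen, with no gain in validity. At n = 100 it would fire on 13-89% of samples with classical critical values and 97-100% with Lilliefors, over assumed SDs of 1.5 to 2.5. Those figures rest on the inferred whole-number 0-10 scale, the assumed mean and SD, and the reading that the test applies to raw values. The omissions in the SAP text rest on none of these.

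Disability is covered by the same rule but is little affected in practice. For TNF-alpha, the point is limited to mild skew, where the test version decides the outcome. The change is worth making before analysis, but the trial's design and sample size do not depend on it.

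**What to change.** Replace the test-then-transform rule in the SAP with the following:
- Analyse pain and disability on their original scales at both visits, and report group differences in scale points.
- Pre-specify log(TNF-alpha/creatinine) for every TNF-alpha analysis. In the model of changes, this means the change in the log ratio.
- Check model residuals descriptively, by plots, with no test that triggers a change of analysis.
- Where residuals are clearly non-normal, add one bootstrap or rank-based sensitivity analysis beside the planned one.

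The cost is a few lines of SAP text and one extra analysis. No further patients or measurements are needed.

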## Project Protocol

### Experimental design

The study consists of a mechanistic randomized placebo-controlled clinical trial with a mixed experimental design, whose objective is to assess which variables that have been linked to central sensitization (CS) in chronic pain patients can predict the response of chronic low back pain (CLBP) patients to spinal manipulative therapy (SMT). In order to do this, clinical, psychophysical and inflammatory variables will be measured in CLBP patients, which will be exposed to either SMT or a placebo SMT for 12 visits over a 4-week period. Another group made up of healthy volunteers will be used to determine the reference values of the same variables in a healthy population and compare them with the clinical population, before and after exposure. The primary outcome measures and main clinical variables are pain intensity and disability. All variables will be measured before the first SMT session, as well as at the end of the twelfth and last session, except for pain intensity, which will be measured at the start of each session for exploratory reasons.

**Figure 1.** Study protocol for the clinical trial

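### Two primary outcomes are named, but the plan sets no testing order, adjustment or rule for primary success; if either may count, the two-sided false-positive risk is about 8% to 10% rather than 5%

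*SAP*

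**What the plan says.** Two outcomes carry primary status throughout.

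- Protocol, Experimental design: "The primary outcome measures and main clinical variables are pain intensity and disability".
- Protocol, Clinical examination variables: "Pain intensity will be the main primary outcome", and later in the same paragraph "The other primary outcome will be the degree of disability provoked by CLBP".
- SAP, Statistical analyses: "The two main outcome variables (clinical pain intensity and disability related to low back pain) will be compared between groups (SMT vs. placebo) over time". The method is a mixed analysis of variance on baseline and session 12. For pain, the analysed variable is average intensity.

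The SAP states no significance level. The only one is in the protocol's Sample size calculation, which uses "an alpha of 0.05, a power of 0.8 for 2 groups and 2 repeated measures" together with f = 0.175 and "a correlation between the repeated measures of 0.5", and concludes that "the size of the necessary sample is 34 patients per group and a total of 68 patients". The planned patient sample is larger, 100 (50 per group), because the regression aim sets it.

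The SAP names two devices for follow-up testing: planned comparisons to break down significant effects, and Tukey's HSD for pairs of group means. It gives the exploratory label to the secondary variables, not to pain or disability.

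**The concern.** With two primary outcomes, a plan has to say how they combine: one is tested before the other, the alpha is shared, or both must succeed. This plan does none of these. Planned comparisons and Tukey's HSD work on group means within an analysis, so they do not control error across pain and disability.

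The gap leaves it open, until the data are seen, whether one significant outcome is enough to call the trial positive. The official title speaks of efficacy, and the protocol states that it expects SMT to beat placebo on both outcomes, so a claim of benefit is foreseeable. If either outcome may carry that claim, the overall false-positive rate exceeds the 5% in the protocol.

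**Working it through.** **Inputs from the documents.** Two primary outcomes; alpha 0.05; power 0.8; f = 0.175; 2 groups; m = 2 measures; correlation between the repeated measures 0.5; 68 patients stated, 100 planned. The F test is non-directional, so 0.05 is two-sided.

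**Input not in the documents.** The correlation r between the pain and disability test statistics, which is in effect the correlation between change in pain and change in disability. The 0.5 in the protocol is a different quantity (baseline against session 12 of the same outcome). I use r from 0 to 0.8 as an assumed range.

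**Step 1: reproduce the stated sample size.** For the group-by-time interaction, the noncentrality is λ = f² × N × m / (1 − 0.5), with 1 and N − 2 degrees of freedom.

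- N = 66: λ = 0.030625 × 66 × 4 = 8.085, power 0.7997.
- N = 68: λ = 0.030625 × 68 × 4 = 8.33, power 0.812.

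The smallest even N reaching 0.80 is 68, as stated. The between-group main effect would need 196, so the protocol's figure is the interaction test at an undivided 0.05. At 0.025 the same 68 patients give power 0.722. The design calculation therefore makes no allowance for a second primary outcome.

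**Step 2: false-positive risk if either outcome counts as success.** With no true effect on either outcome, the two-sided risk is 1 − P(|Z1| < 1.96 and |Z2| < 1.96) for a bivariate normal with correlation r. At r = 0 this is 1 − 0.95² = 0.0975. The risk of a false result favouring SMT on at least one outcome is 1 − P(Z1 < 1.96 and Z2 < 1.96), with positive Z favouring SMT. At r = 0 this is 1 − 0.975² = 0.0494.

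| Assumed r | Either outcome, two-sided | Either outcome, favouring SMT |
|---|---|---|
| 0 | 9.75% | 4.9% |
| 0.3 | 9.5% | 4.8% |
| 0.5 | 9.1% | 4.5% |
| 0.7 | 8.3% | 4.2% |
| 0.8 | 7.8% | 3.9% |

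The nominal values for a single outcome are 5% and 2.5%. The two-sided rate falls to 5% only at r = 1.

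**Step 3: what control would cost at the planned 100.** These figures assume f = 0.175 for both outcomes and complete data on all 100 patients.

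- Pain first at 0.05: λ = 0.030625 × 100 × 4 = 12.25, power 0.934 for pain. By simulation, both outcomes succeed with probability 0.88 (r = 0.3) to 0.90 (r = 0.7). Familywise error is at most 5%.
- Bonferroni at 0.025 each: 82 patients are needed for power 0.80 per outcome. At 100, power is 0.888 per outcome. Familywise error is at most 5% (4.9% at r = 0, 4.7% at r = 0.5).

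**The case against.** The case against has five parts.

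1. **Nothing says that one significant outcome is enough.** The sample size paragraph speaks of pain and disability together, which could be read as requiring both. Under such a rule the chance that both are falsely significant, with no effect on either, is only 0.25% (r = 0) to 1.7% (r = 0.7). This stands in part: the either-outcome rule is a reading, not a quotation. But no section requires both, so the gap is the missing rule itself.
2. **The SAP does not state 0.05 per outcome.** That is correct. It is inferred from the sample size paragraph and supported by the reproduced 68.
3. **A reader might infer that an ineffective treatment has about a 9% chance of a false efficacy claim.** The documents do not support that. The two-sided rate counts results in favour of placebo as well, while the protocol expects benefit from SMT. The risk in that direction is 4.9% to 3.9%, and even this depends on an assumed correlation.
4. **A reader might infer that the protocol has already settled the order, because it calls pain the main one.** It has not. That is a label in one section. The Experimental design section and the SAP present the two outcomes side by side, and no testing consequence is attached. The label does make pain-first the natural choice.
5. **The trial is described as mechanistic, and prediction is its first aim.** This lowers the consequence, and with only two named outcomes a reader can see the multiplicity. It does not remove the issue, because the trial also sizes an SMT-placebo comparison and has efficacy in its title.

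**Conclusion.** The concern holds in a limited form: the plan has two primary outcomes and no stated rule for primary success. If either outcome may count, and each is tested at two-sided 0.05, the chance of at least one false primary result is 9.75% to 7.8% for assumed correlations of 0 to 0.8. The part favouring SMT is nearly double its nominal rate at low correlation and about one and a half times at 0.8 (3.9 / 2.5 = 1.56). The exact size rests on a correlation that the documents do not give, but the direction does not: there is inflation at any correlation short of 1. This is a gap in the primary inference that should be closed. It does not invalidate the design, and the planned sample is large enough for any of the usual remedies.

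**What to change.** Add to the SAP, before unblinding: the group-by-time effect on average pain intensity is tested first at two-sided 0.05; disability is tested at two-sided 0.05 as a confirmatory outcome only if pain is significant; otherwise disability is reported with its confidence interval and without an efficacy claim. This order follows the protocol's own description of pain.

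If the sponsor regards the two outcomes as equal, Holm or Bonferroni can be specified instead; the planned 100 exceeds the 82 that Bonferroni needs. If the intention is that both must be significant, the SAP should say so, and that would also remove the inflation.

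The cost is a short addition to the SAP and no extra patients. The downside of the pain-first order is that no confirmatory claim on disability can be made if pain fails. The protocol states no dropout allowance, so the power figures for 100 would fall with missing data.

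### The mixed ANOVA of pain and disability is valid, but an ANCOVA on the baseline score already collected is more precise; the predictor regressions would be clearer with a baseline-adjusted version beside them

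*SAP*

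**What the plan says.** **Primary comparison.** Under Statistical analyses, the SAP says that pain intensity and disability "will be compared between groups (SMT vs. placebo) over time (baseline and session 12) using a mixed analysis of variance". It mentions no baseline covariate, no ANCOVA and no baseline-adjusted sensitivity analysis. The protocol (Clinical examination variables) confirms that for pain "only the baseline and the final values will be used for statistical analyses". The pain measure has different recall windows at the two times: "Average pain intensity since the previous treatment visit and in the seven days prior to the initial visit will be the variable used".

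The protocol (Sample size calculation) sizes this comparison with f = 0.175, alpha 0.05, power 0.8 and "a correlation between the repeated measures of 0.5". This gives 34 per group, 68 in total. The planned 50 per group comes from a separate rule of about ten patients for each of five regression predictors.

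**Predictor regressions.** The SAP then looks for "predictors of improvement in clinical pain and disability over time in patients who have received SMT". It says that these models are to be built "using secondary variables with a significant association with the primary variables". It goes on: "The secondary variables used for this analysis will be: baseline PCS and CSI score, baseline PPTs in the primary pain region", followed by baseline TNF-alpha and expectations of relief. A further model uses the changes in these variables, without expectations. Baseline pain or disability enters none of these models. The SAP does not say whether improvement means absolute change, percent change or something else.

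**The concern.** With only baseline and session 12, the group-by-time F test is the same test as a t-test comparing change from baseline. A change score subtracts the whole baseline value. When the correlation between the two scores is well below 1, that adds noise which ANCOVA avoids by subtracting only the predictable part. The trial therefore gives up precision on both primary outcomes although it holds the data needed to recover it.

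The regressions raise a related, weaker point. If improvement is a change score, patients with high baseline scores tend to improve more through regression to the mean. A predictor correlated with baseline severity can then look predictive without carrying any information beyond that severity. Finding predictors of response is the trial's first aim, so a reader will want to see whether a result depends on how baseline severity is handled.

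**Working it through.** **1. Reproduce the plan's figure.** Inputs from the protocol, Sample size calculation: f = 0.175, correlation rho = 0.5, two groups, two measures, alpha 0.05. For the group-by-time interaction, lambda = f² × N × 2/(1 − rho). At N = 68, lambda = 0.030625 × 68 × 2/0.5 = 8.33, and power is 0.812. At N = 66 power is 0.7997, so 68 is reproduced.

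**2. Convert the effect.** A change-score t-test has lambda = N × d²/[8(1 − rho)]. Setting this equal to step 1 gives d = 4f = 0.70 SD. The plan has therefore sized a change-score test.

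**3. Compare variances (in units of the outcome variance, equal SDs).** Change score: 2(1 − rho). ANCOVA: 1 − rho². The ratio is (1 + rho)/2. At 50 per group:

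| rho | Change | ANCOVA | Saving | Power at 0.70 SD | Detectable difference, 80% power (SD) |
|---|---|---|---|---|---|
| 0.3 (assumed) | 1.40 | 0.91 | 35% | 83% to 95% | 0.67 to 0.54 |
| 0.5 (protocol) | 1.00 | 0.75 | 25% | 93% to 98% | 0.57 to 0.49 |
| 0.7 (assumed) | 0.60 | 0.51 | 15% | 99.4% to 99.8% | 0.44 to 0.40 |

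**4. Charge ANCOVA for its cost.** One degree of freedom is lost, and chance baseline imbalance inflates the variance by 1 + 1/(N − 4) = 1 + 1/96. The ratio at rho = 0.5 becomes 0.75 × 1.0104 = 0.758. The confidence interval width ratio is 0.87, so about 13% narrower (0.81 at rho 0.3, 0.93 at rho 0.7). Power is 0.978 instead of 0.979. The gain vanishes only at rho of about 0.98.

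**5. Unequal SDs.** The change-score variance minus the ANCOVA variance is (SD at baseline − rho × SD at final)², which is never negative. If the final SD were 0.8 or 1.2 times the baseline SD (assumed), the saving at rho 0.5 would be 43% or 13%.

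**6. Regressions.** Assume improvement is baseline minus session 12, with equal SDs. Its correlation with the baseline score is √[(1 − rho)/2] = 0.50 at rho = 0.5. Simulation used n = 50, five predictors, one of them correlated r with baseline, and 20,000 runs per cell. The documents give no values of r, so these are assumptions. Share of trials in which that predictor is significant at 5%:

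| Scenario and model | r = 0.2 | 0.3 | 0.4 | 0.5 |
|---|---|---|---|---|
| Nothing beyond observed baseline: planned predictors | 10% | 17% | 27% | 39% |
| Same, after a correlation screen at p < 0.05 | 8% | 14% | 24% | 36% |
| Same, baseline outcome added | 5% | 5% | 5% | 5% |
| Predictor tracks a stable pain level: planned predictors | 5% | 5% | 5% | 5% |
| Same, baseline outcome added | 12% | 23% | 40% | 62% |

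The screened row is one reading of the SAP's selection step. The SAP's further filter on significant group-over-time effects was not simulated. The model based on changes in the predictors is much less affected: 7%, 8%, 10% and 13%, assuming a correlation of 0.5 between each predictor's own two measurements.

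**The case against.** **The primary analysis is not defective.** This stands. The mixed ANOVA is unbiased under randomisation, and at the plan's own effect 50 per group already gives 93% power. ANCOVA would need 26 instead of 34 per group for 80% power, but the planned 50 is set by the regression rule and does not change. A reader might infer that the planned analysis is wrong or underpowered; the documents support neither.

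**A larger benefit at smaller effects.** A reader might take "We aim to detect small to moderate effects since it is a one-month intervention in patients with chronic pain" to mean that effects well below 0.70 SD are targeted. In the protocol that sentence leads directly to f = 0.175, which is the 0.70 SD case. At 0.5 SD, power would go from 70% to 82%, but that effect is an assumption and not the plan's. Likewise, the different recall windows make unequal SDs possible but do not show them.

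**The regressions do not need adjustment.** This also stands. If a predictor tracks a stable pain level, the planned model is correct and the adjusted one misleads. The documents do not say which situation applies, so the case is for showing both models, not for replacing one.

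**Requiring agreement between the two models.** A reader might infer that a predictor should count only if significant in both, and otherwise be called inseparable from baseline severity. That is unsound. Simulate a true predictor (partial correlation 0.4 with improvement) that is unrelated to baseline. The planned, adjusted and both-significant rates are 0.665, 0.792 and 0.640, so the models disagree in 0.665 + 0.792 − 2 × 0.640 = 17.7% of trials. At a correlation of −0.3 with baseline the figure is 0.229 + 0.796 − 2 × 0.229 = 56.7%. Such a rule would also give a six-term model, which falls short of the protocol's ten-per-predictor rule, a veto over the one that meets it.

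**Conclusion.** The primary point holds as a gain in precision, not as the correction of an error. At rho = 0.5 and equal SDs the variance falls by about 25% and the interval narrows by about 13%. Power at 0.70 SD goes from 93% to 98%, and the detectable difference from 0.57 to 0.49 SD. The saving ranges from 35% at rho 0.3 to 15% at rho 0.7. Confidence in this arithmetic is high, since it uses the protocol's own inputs and reproduces its sample size.

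The regression point is a secondary suggestion. The figure of about 17% false positives applies before screening. It assumes that improvement is an absolute change score, a correlation of 0.3 with baseline, rho of 0.5, and a predictor that carries nothing beyond the observed baseline. Under a stable-level model the planned regression is the sound one.

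**What to change.** **Main change (SAP, Statistical analyses).** Analyse session-12 pain, and final disability, by ANCOVA with group and the baseline value of the same outcome as terms. Keep the mixed ANOVA as a sensitivity analysis. Cost: SAP wording and one degree of freedom; no new data and no change to the 50 per group.

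**Secondary suggestion.**
- Define improvement as change from baseline to session 12, and say whether it is absolute or percent.
- Keep the planned regressions. Beside each, report a version with the baseline value of the outcome added.
- Present both estimates with confidence intervals and discuss any difference. Do not require both to be significant, and do not label a predictor because the two disagree in significance.
- State the limits of the adjusted version. With baseline predictors it has six terms, 50/6 = 8.3 patients per term, where the protocol's rule would ask for 60 patients. It can also flag a pure severity marker under a stable-level model. The adjusted version of the change-based model has five terms (50/5 = 10) and stays within the rule.
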